Appendix 12 – Guideline for thromboembolic events

A) Suspicion of venous thrombosis related to the catheter

Appendix 12 – Guideline for Thromboembolic Events

B) Pulmonary thromboembolism (PTE) suspicion

1 AMENDMENTS FROM PREVIOUS VERSION(S)

Not applicable. This is version 1.0 of the SAP.

2 INTRODUCTION

Note: in this document any text taken directly from the protocol is *italicized*. This SAP described the analysis that is planned for the final analysis of the study data.

2.1 STUDY DESIGN

A clinical trial comprised of 364 subjects with probable mild to moderate AD will be conducted primarily to determine whether short-term followed by long-term, low-volume plasma exchange with human albumin combined with IVIG is able to modify patient's cognitive, functional, behavioral and global domains. There will be 3 treatment groups and one control group. The subjects will be randomized in a 1:1:1:1 proportion.

After screening and randomization, treatment groups will proceed as follows:

- *One month and a half (6 weeks) of intensive treatment with one plasma exchange per week. All 3 treatment groups are the same during the intensive treatment phase.*
- *Two of the three groups will follow 12 months of maintenance treatment with one low-volume plasma exchange every month combined with IVIG every 4 months administered at the end of the corresponding plasmapheresis instead of albumin (that is, 9 plasmaphereses with Albumin replacement and 3 plasmaphereses with IVIG replacement). During this year, treatment-group patients will follow one of the two different pre-allocated treatment arms: 1) with the doses of albumin and IVIG needed to replace those removed during the plasmapheresis, 2) with half of the doses of albumin and IVIG.*
- *One of the three groups will follow the same schedule as the above two groups but with half of the doses of albumin alone (without IVIG), that is, 12 plasmaphereses with half-dose albumin alone.*

Patients in the control group will undergo sham procedures mimicking plasmaphereses but with neither fluid exchange nor albumin or IVIG administrations.

There are also a total of 18 patients who completed the study under protocol Version 1.0. The treatment under Version 1.0 of the protocol was not blinded but the treatment schema was similar to protocol Version 2.0 or later versions. Because there was no sham treatment in Version 1, the randomization date will be used as study start date for the

	Title: Statistical Analysis Plan
	Project #: IG1002 AMBAR
	Version: Final 1.0 Effective Date: 31July2018
	Protocol Version: Version 5.0 Effective Date: Feb2018

control patients. However, according to Version 1.0, laboratory values have only been assessed at Baseline, the intermediate visit, LVPE4, LVPE7, LVPE10, and the final Visit. The data from all protocols will be combined for the final analysis wherever possible. These study patients treated under protocol Version 1.0 will be combined to the treatment groups from protocol Version 2.0 or later versions of the protocol as follows:

- Treatment arm A: (100% albumin+Flebo V1.0) + (100% albumin+Flebo V2.0)
- Treatment arm B: (1/2 albumin+Flebo V1.0) + (1/3 albumin+Flebo V1.0) + (1/2 albumin+Flebo V2.0)
- Treatment arm C: (1/2 albumin V2.0)
- Treatment arm D (no treatment): (Control V1.0) + (Sham V2.0)

where V2.0 is protocol Version 2.0 or later versions.

A sample size of 312 subjects (78 per each of the 4 groups) will make it possible to detect with nearly 92% power for the first of the co-primary efficacy variables (the changes from baseline of the ADAS Cog scores) a difference in the mean of 3 points between any of the treatment groups and the control group, assuming the common standard deviation (SD) to be 5.55 (according to the data obtained in the phase II study), with a level of significance of 5%. This same sample size provides over 98% power for second of the co-primary end point variables (the changes from baseline of the ADCS-ADL scores) a difference in the mean of 6.69 points between any of the treatment groups and the control group, assuming the common standard deviation (SD) to be 10.0 (according to the data obtained in the phase II study), with a level of significance of 5%.

The study will have joint power for these co-primary end points of at least 90% ($0.92 \times 0.98 = 0.90$). The calculation makes the conservative assumption that these end points are independent. Since these end points are positively correlated 90% should serve as a lower bound on power.

Assuming a global dropout rate of approximately 15%, the study would have to enroll 364 subjects to obtain 312 subjects for evaluation.

2.2 STUDY OBJECTIVES

Primary objective:

To evaluate the changes in the cognitive, functional, behavioral and global domains based on the different applicable psychometric batteries and scales.

Secondary objectives:

	Title: Statistical Analysis Plan
	Project #: IG1002 AMBAR
	Version: Final 1.0 Effective Date: 31July2018
	Protocol Version: Version 5.0 Effective Date: Feb2018

- *To determine the changes in the concentration of beta-amyloid peptide in plasma and cerebrospinal fluid (CSF) in the treatment group of patients with Alzheimer's disease (AD).*
- *To evaluate the structural changes in volume of the hippocampus, posterior cingulate area, and other associated areas based on neuroimaging studies with Magnetic Resonance Imaging (MRI) (variations versus baseline).*
- *To determine functional brain functional changes through FDG-PET (fluorodeoxyglucose-PET).*
- *To determine whether plasma exchange with human albumin combined with intravenous immunoglobulin (IVIg) is safe, taking into account the following factors:*
 - *Type, severity and frequency of adverse reactions during and after the procedure and infusions.*
 - *Changes in vital signs and clinically relevant changes, according to the laboratory test findings. –*
 - *Control of episodes of cerebrovascular accidents with MRI.*

3 INTERIM ANALYSES, FINAL ANALYSES AND UNBLINDING

Unblinding of the study data and final analysis will be performed after the study database has been declared clean and has been locked.

4 HYPOTHESES AND DECISION RULES

[figure not shown]
4.1 STATISTICAL HYPOTHESES

The null hypothesis for each test is that drug response is equal to placebo response, and the two-sided alternative is that drug response is not equal to placebo response.

4.2 STATISTICAL DECISION RULES

The statistical tests will be performed with a 5% significance level and will be two-sided. In addition to the tests, two-sided 95% confidence intervals (95% CI) will be reported.

Because the end points are co-primaries, both must be statistically significant for the study to provide evidence of efficacy. Therefore, no multiplicity adjustment is needed to adjust for the co-primary end points. However, to account for the three dose group comparisons to placebo and to maintain the overall significance level of 0.05, adjustment for α will be made for multiple dose groups according to the Hochberg¹ procedure. The

	Title: Statistical Analysis Plan
	Project #: IG1002 AMBAR
	Version: Final 1.0 Effective Date: 31July2018
	Protocol Version: Version 5.0 Effective Date: Feb2018

Hochberg procedure will be implemented as follows: For each end point, the three dose group comparisons versus placebo will be ordered according to the p-value from the largest to the smallest. If the largest p-value is < 0.05 then all comparisons to placebo will be declared significant. Otherwise, if the second largest p-value is < 0.025 (0.05/2) then this dose and all doses with smaller p-values will be declared significant. Otherwise, if the smallest p-value is < 0.0167 (0.05/3) then this dose will be declared significant. Otherwise, no dose is considered significantly different from placebo. This procedure has been demonstrated to control the overall Type I error at 0.05. Both co-primary end points must be significant at a given dose to provide evidence of efficacy for that dose.

Specifically, the null hypothesis for all inferential analyses, including the primary end points, is that all three treatment groups are equal to placebo. Specific doses will be considered different from placebo if statistically significant following the Hochberg procedure described above. The study is considered positive if at least one dose group differs from placebo in both of the co-primary analyses. Subsequently, secondary end points are considered positive if at least one dose group differs from placebo.

A supportive analysis will be performed in per protocol analysis set for each of the co-primary efficacy end points applying the same respective methodologies, but without adjusting for Type I error.

[figure not shown]
Secondary end points are also controlled for the three dose comparisons by the method of Hochberg, but there is no formal control for multiple secondary end points; each is tested at overall significance level of 0.05. Interpretation will be based on the weight of the evidence and the totality of the data.

5 ANALYSIS SETS

5.1 FULL ANALYSIS SET (FAS)

All subjects included in the study and subjected to at least one plasma exchange session (i.e., randomized and treated) during the intensive treatment phase (the six first weeks of treatment) will form part of the efficacy population.

Control group subjects will also be included (without the plasma exchange) if they attended at least 1 of the 6 intensive treatment phase visits. For the control group from protocol version 1, patients will be included in the FAS if they have at least the intermediate visit performed.

	Title: Statistical Analysis Plan
	Project #: IG1002 AMBAR
	Version: Final 1.0 Effective Date: 31July2018
	Protocol Version: Version 5.0 Effective Date: Feb2018

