5.1.3 Method of Application

Full plasma exchanges (Intensive treatment period)

Full plasma exchanges (FPE) can be carried out via peripheral access or centrally, according to the individual characteristics of the subject. In the latter case, and before the first replacement session, a double-lumen catheter must be placed in the subclavian or jugular vein. Implantation and maintenance will be carried out according to the standard procedures used in each center but it will be mandatory to perform a chest X-ray to confirm the correct placement of the catheter. Removed plasma volume will be replaced with the same volume of Albutein[®] 5% during the procedure.

The removed and replaced plasma volume will depend on patient's characteristics (sex, height, weight and hematocrit). It will be approximately 35-45 mL/kg, corresponding to a volume of 2500-3000 mL. This volume is calculated automatically by the device or manually by the operator depending on the device used.

For blinding the control group, adhesive gauze dressing will be placed on the subclavicular or jugular region, stitching a catheter of characteristics similar to the catheters used in the treatment group (see Appendix 9).

The central catheter has the advantage of increased convenience for the subject during the process, since it allows greater flows and thus shorter session times and obviates the need in each session to perform two peripheral venipunctures. The central line access also facilitates subject mobility during the procedure.

Each session is carried out at a rate of 60-100 mL/min., provided replacement is possible through a double-lumen catheter placed in the subclavian vein, with a continuous-flow cell separator. Each of these sessions will last approximately two to three hours. The control group will be subjected to simulated (sham) plasma exchanges during the same time as the subjects in the treatment group.

Each subject must remain in the facility throughout the procedure and then for as long as necessary to ensure a safe return home.

These details refer to the plasma exchange procedure performed through centrifugation (the most commonly used) although the procedure through filtration is also permitted.

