5.4 TREATMENT MISALLOCATIONS

For subjects with errors in treatment allocation, they will be reported for efficacy and safety analyses as follows:

If a subject was:

- Randomized but not treated (treatment is defined as attending post baseline study visits), then they are by definition excluded from the efficacy and safety analyses as actual treatment is missing.
- Treated but not randomized, then by definition they will be excluded from the efficacy analyses since randomized treatment is missing, but will be reported under the treatment they actually received for all safety analyses.
- Randomized but took incorrect treatment, then they will be reported under their randomized treatment group for all efficacy analyses, but will be reported under the treatment they actually received for all safety analyses.

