9.2 STATISTICAL ANALYSES

9.2.1 Primary Analysis

The primary analysis is based on the FAS population and the primary end points of 1) change from baseline in the Total ADAS-Cog change from baseline score and 2) change from baseline in the ADCS-ADL inventory score at month 14 using MMRM as described in Section 9.1.1 above.

To support the interpretation of the primary analysis, an identical analysis as described above, based upon the PP population rather than the FAS, will be conducted.

The co-primary end points ADAS-Cog and ADCS-ADL will also be analyzed by AD severity as defined in Section 7.4. The same primary analysis will be performed as for the entire population with the exception that the MMRM will not be adjusted for AD severity.

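### Entry to the primary efficacy set needs a delivered exchange in the active arms but only visit attendance in the control arm

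*SAP*

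**What the plan says.** SAP 5.1 sets two entry conditions for the full analysis set (FAS). The general one is "All subjects included in the study and subjected to at least one plasma exchange session (i.e., randomized and treated) during the intensive treatment phase". The control condition is different: "Control group subjects will also be included (without the plasma exchange) if they attended at least 1 of the 6 intensive treatment phase visits". No sham session has to be delivered. Protocol 10.1.1 has the same split.

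SAP 5.4, on treatment misallocations, uses another criterion and does not distinguish arms: "Randomized but not treated (treatment is defined as attending post baseline study visits), then they are by definition excluded from the efficacy and safety analyses".

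The choice of set matters because "The primary analysis is based on the FAS population" (SAP 9.2.1). In the table in SAP 9.2.5, every efficacy analysis uses the FAS or the per-protocol set. None uses all randomised patients.

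**The concern.** Membership of the primary set depends on an event after randomisation, and the event differs by arm. An active patient must have an exchange delivered. A control need only attend.

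The step between attending and receiving an exchange is not the same in the two conditions. For central access, Protocol 5.1.3 requires that "before the first replacement session, a double-lumen catheter must be placed in the subclavian or jugular vein", and Protocol 6.2.1 advises doing this some days ahead. Controls have a catheter mounted on a skin patch and not inserted (Appendix 9, section 1). Protocol 5.2.1 holds a real exchange when coagulation or platelet values fall outside set limits. Appendices 11 and 12 make catheter removal for infection, or any thromboembolic complication, a reason for withdrawal. A sham patient has no inserted central catheter and no plasma removal to set these off.

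At stake is the comparability of the randomised groups in the two co-primary tests. Patients lost between attendance and first exchange drop out of the active arms, and patients with the same attendance stay in the control arm. No planned efficacy analysis would show the effect.

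**Working it through.** **1. The rules side by side**

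| Patient | SAP 5.1 | SAP 5.4 |
|---|---|---|
| Active, attends, at least one exchange in the first six weeks | in FAS | treated |
| Active, attends more than one intensive visit, no exchange | out | treated |
| Active, attends week 1 only, no exchange | out | unclear |
| Control, same attendance as either row above, no sham delivered | in FAS | same reading as that row |
| Any arm, attends no intensive visit | out | not treated, if no later visit is attended |

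Row 3 is unclear because SAP 7 places day 1 both in the baseline window and at the first exchange visit, so a week 1 visit may not count as after baseline. Rows 2 and 3 against row 4 are the asymmetry. Row 2 is the clear conflict between 5.1 and 5.4.

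**2. The plan's own power figures**

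Inputs from SAP 2.1: 78 per arm; ADAS-Cog difference 3, SD 5.55; ADCS-ADL difference 6.69, SD 10.0; two-sided 5%. Power = Φ(difference / SE − 1.96), with SE = SD × √(2/78).

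- ADAS-Cog: SE = 0.889; 3 / 0.889 = 3.376; power 0.922 (noncentral t 0.918). The plan says nearly 92%.
- ADCS-ADL: SE = 1.601; 6.69 / 1.601 = 4.178; power 0.987 (noncentral t 0.986). The plan says over 98%.
- Joint, as a product: 0.909. The plan says at least 90%.

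All three reproduce.

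**3. How many patients**

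364 randomised 1:1:1:1 gives 91 per arm and 273 active. The documents give no rate of attending without an exchange, so f is an assumption: 1% is 2.7 patients of 273, 2% is 5.5, 5% is 13.7, 10% is 27.3.

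**4. Effect on power**

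With the active arm cut to 78 × (1 − f), SE = SD × √(1/78 + 1/(78(1 − f))).

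- f = 5%: ADAS-Cog 0.915, ADCS-ADL 0.985.
- f = 10%: ADAS-Cog 0.908, ADCS-ADL 0.982.

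Power is not the issue.

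**5. Effect on the estimate: a worst-case illustration**

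Suppose the removed patients differed from those retained by d at month 14, and that the whole difference counted. The shift in the active mean is f × d. With d assumed to be 1 SD:

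| f | ADAS-Cog shift | ADCS-ADL shift | Type I error, one 5% comparison |
|---|---|---|---|
| 2% | 0.11 | 0.20 | 5.2% |
| 5% | 0.28 | 0.50 | 6.1% |
| 10% | 0.56 | 1.00 | 9.6% |

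The error is Φ(−1.96 + shift/SE) + Φ(−1.96 − shift/SE). At 5% for ADAS-Cog, 0.278 / 0.889 = 0.312.

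These figures overstate the case for patients who leave early. SAP 7 assigns efficacy scores by collection date, so a score on days 2 to 93 goes to the intermediate visit, not month 14. It reaches the month-14 contrast only through the covariance structure of the mixed model in SAP 9.1.1. The table is not an estimate of the actual bias, nor of the error of the whole procedure, which needs both endpoints and uses Hochberg.

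**The case against.** The strongest reply is that the affected group is narrow. Protocol 5.2.1 postpones or suspends an exchange and does not remove the patient, and six sessions are scheduled. Screening already excludes difficult venous access and low platelets, prothrombin and fibrinogen (Protocol 4.1.2). Sham sessions also need a real peripheral line (Appendix 9), so the two conditions are not wholly unlike. All this stands, and it limits the number. It does not explain why the rule should differ by arm.

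Second, SAP 5.4 is an exclusion rule and SAP 5.1 defines the set, so a patient could pass the first and fail the second. That is a fair reading, but one plan then has two meanings of treated. The table of patients randomised but not treated (SAP 6.1), which might otherwise give transparency, inherits the ambiguity.

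Third, few excluded patients may have a usable score. Protocol 4.4 schedules a final visit with tests after withdrawal, but Protocol 6.2.5 lets some assessments be skipped if that visit is early. This stands, and it is why the effect on the primary contrast is described as indirect. In the last-observation-carried-forward ANCOVA listed in SAP 9.2.5, however, such a score would be carried to month 14.

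Four stronger readings are tempting and not supported:

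- **That patients who stop before the first exchange are lost from the active arms only.** A control who attends no intensive visit is excluded too.
- **That the removed patients are frailer, so the bias favours treatment.** The documents say nothing about their prognosis.
- **That Version 1.0 controls, for whom "patients will be included in the FAS if they have at least the intermediate visit performed", add a further distortion.** The SAP says "There are also a total of 18 patients who completed the study under protocol Version 1.0", so the rule should exclude none of them. Version 1.0 had no sham sessions to attend.
- **That the choice of rule is left open until the data are seen.** SAP 5.1 is the named FAS definition and agrees with the protocol.

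**Conclusion.** The point holds in a limited form. As written, the primary efficacy set applies a delivery condition to active patients and an attendance condition to controls, and SAP 5.4 disagrees with the first. The resulting exclusion can depend on the assigned arm.

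Its size cannot be determined from the documents. The count of about 3 to 14 active patients rests on an assumed 1% to 5%, and any shift in the estimate rests on a further assumption about how those patients differ. Power is essentially unaffected. The direction of any bias is unknown, and its route to the month-14 comparison is indirect. The correction should still be made, because different entry rules by arm serve no analytic purpose and one symmetric rule removes the problem.

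**What to change.** Before database lock, define the FAS by one rule for all arms.

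- **Preferred:** all randomised patients, analysed as randomised. The mixed model then uses those with a post-baseline score. This also covers active patients lost at catheter placement, whom an attendance rule would still miss.
- **Minimum:** all randomised patients who attended at least one of the six intensive-phase visits, whether or not an exchange or sham was delivered. This avoids SAP 5.4's phrase about post-baseline visits, which is ambiguous for day 1.

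State that the scheduled first exchange visit is the Day 1 reference for a patient with no exchange. SAP 7 otherwise ties Day 1 to the first treatment received, although it already anchors efficacy visit assignment to the first exchange visit regardless of treatment deviations. Bring SAP 5.4 and Protocol 10.1.1 into line, and report by arm the numbers randomised, attending and exchanged.

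The cost is SAP and protocol wording plus one short table. The downside is that a few untreated active patients enter the efficacy set, which is slightly conservative.

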5.2 PER PROTOCOL ANALYSIS SET (PP)

A second efficacy analysis will also be carried out (per protocol analysis) with the patients who complete the treatment without major breaches in the study protocol.

5.3 SAFETY ANALYSIS SET

All patients included in the study and subjected to at least one plasma exchange session will form part of the safety population.

Control group subjects will also be included (without the plasma exchange) if they attended at least 1 of the 6 intensive treatment phase visits. For the control group from protocol version 1, patients will be included in the safety population if they have at least the intermediate visit performed.

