5.2.2.5 AEs Related to vascular access

The central catheter has the advantage of increased convenience for the subject during the process, since it allows greater flows and thus shorter session times, obviating the need in each session to perform two peripheral venipunctures.

As to the adverse effects if the catheter is placed in the subclavian vein, the risk of infection is minimal. Thus, while the incidence of infections with all the catheters is <5 per 1000 days (<3% of all catheters), this incidence decreases considerably if only those placed in the subclavian vein are considered^{23,24}. Pneumothorax, hemothorax, bleeding at the time of placement and thrombosis in the case of indwelling catheters left in place for extended periods of time may be seen. The recommendations for the treatment and prevention of fever management and thromboembolic events have been captured in two study guidelines (see Appendix 11 and Appendix 12, respectively); nonetheless the sites should follow their local procedures.

As to adverse events related to peripheral access, the most commonly expected are: pain, phlebitis, infiltration and extravasation.

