At the same time, during this study period (from week -3 to week 0), the following tests will be administered to measure cognition, functionality, behavior, global evolution, impression and depression : MMSE, ADAS-Cog, NPS battery, ADCS-ADL, NPI, CDR-Sb, ADCS-CGIC, CSDD, CSSRS, QoL-AD and RUD-Lite[®] which are to be administered as indicated in the corresponding section. Likewise, anxiety and restlessness tests will be made based on the Overt Aggression Scale (OAS) and the Agitated Behavior Scale (ABS), whenever considered opportune.

If the subject is to receive full plasma exchanges through a central venous access, a double-lumen catheter will be placed in the subclavian or jugular vein before the full plasma exchange period. It is advisable to place the catheter a few days before the first plasma exchange session. For the low-volume exchanges peripheral access will be used.

Furthermore, it is obligatory to perform lumbar puncture before the first plasma exchange, to collect CSF samples and assess the levels of A β -40, A β -42, P-tau, T-tau, β -secretase, γ -secretase, cholesterol, LDL, HDL, VLDL, C-reactive protein, IL-1b, IL-6, ferritin, TNF- α) and to perform standard CSF tests (cell counts, glucose, proteins and albumin). Time collection for the CSF must be between 8am and 12am. If these procedures are not carried out in the days preceding plasma exchange, they will have to be done on the day of first plasma exchange with the subject remaining at rest until indication by the investigator that plasma exchange can be carried out. These evaluations are considered to be the baseline data.

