7 END POINTS AND COVARIATES

Baseline is defined as the last assessment prior to study drug administration (first full plasma exchange or sham treatment in the control group).

Most summaries will include the 4 treatment groups and cover the entire study period (including both the intensive and maintenance phases), but some analyses (particularly safety) may summarize a specific phase. Summary statistics will be provided for the

	Title: Statistical Analysis Plan
	Project #: IG1002 AMBAR
	Version: Final 1.0 Effective Date: 31July2018
	Protocol Version: Version 5.0 Effective Date: Feb2018

actual value and for the change from baseline for each point in time a variable is measured. Only available data will be included in these summary statistics, if not otherwise stated, no substitution of missing values will be done. In addition to the analysis at each point in time a variable is measured, for the safety variables and the biomarkers an analysis will also be performed for the last non-missing post-baseline value (end point).

Study days will be numbered relative to the first day of study drug administration. The start of treatment (Day 1) is defined as the date on which a patient receive the first study treatment. Days will be numbered relative to study start (i.e., ..., -2, -1, 1, 2, ...; with day 1 being the first administration of study treatment and day -1 being the day before the first administration of study treatment).

Protocol-defined efficacy assessments will be “slotted” to study visits based on collection date and applying the rules summarized in the following table. The study day range is the time period where assessments can be selected to populate a study visit, e.g. the assessments from study day 92 to study day 228 can be considered as assessments for the LVPE Visit 4 (month 6) visits.

Visit	Target Study Day	Study day range
Screening/Baseline		$-\infty$ to 1
FPE Visit 1 (Week 1)*	1	1
Intermediate visit (Week 7-8)	45	2 to 93
LVPE Visit 4 (Month 6)	141	94 to 184
LVPE Visit 7 (Month 9)	225	185 to 268
LVPE Visit 10 (Month 12)	309	269 to 343
Final Visit	375	344 to ∞
* Reference date for all other visits		

The slotting scheme for the CSF biomarkers will be as follows:

Visit	Target Study Day	Study day range
Screening/Baseline		$-\infty$ to 1
FPE Visit 1 (Week 1)*	1	1
Intermediate visit (Week 7-8)	45	2 to 187
Final Visit	375	188 to ∞
* Reference date for all other visits		

	Title: Statistical Analysis Plan
	Project #: IG1002 AMBAR

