7.2 SAFETY END POINTS

The primary criterion of safety will be the percentage of plasma exchanges (full and low volume exchanges, including the infusion of albumin and IVIG) associated with at least one adverse event that may be related to the study procedure (adverse reactions). In addition, consideration globally will be made of the percentage plasma exchanges (full and low-volume exchanges, including the infusion of albumin and IVIG) involving some adverse event, whether or not related to the procedure.

Vital signs (blood pressure, heart rate, respiration rate, and body temperature) will be recorded before, during and after each plasma exchange session, where required. Evaluation will also be made (where required) of the different laboratory test parameters (blood cell counts, platelet count, prothrombin time (Quick), fibrinogen, total proteins, and calcium).

During the treatment periods (before each plasma exchange) and on the days when there is no replacement, anxiety and restlessness tests will be made based on the Overt

	Title: Statistical Analysis Plan
	Project #: IG1002 AMBAR
	Version: Final 1.0 Effective Date: 31July2018
	Protocol Version: Version 5.0 Effective Date: Feb2018

Aggression Scale (OAS) and the Agitated Behavior Scale (ABS), whenever considered opportune.

According to the criterion of the investigator, all the clinically important changes in vital function, laboratory test parameters and neuroimaging findings will be evaluated. Any adverse events occurring following start of treatment will be counted as treatment emergent.

The analysis of tolerability will be based on description of the safety variables according to their nature.

The adverse reactions will be coded according to the adverse events classification of the World Health Organization (WHO) (MedDRA current version), and will be described by a synonym (Preferred Term) and the affected organ / system, the intensity, causality and seriousness.

The safety population will be used for all safety summaries unless otherwise noted. Summaries will be presented by treatment group and overall unless otherwise noted.

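### Safety set and treatment-emergent window open at the first exchange, after the real central line has been placed in central-access active patients

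*SAP*

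**What the plan says.** **Who is in the safety set.** For active patients, SAP 5.3 says "All patients included in the study and subjected to at least one plasma exchange session will form part of the safety population". For controls the test is attendance: "Control group subjects will also be included (without the plasma exchange) if they attended at least 1 of the 6 intensive treatment phase visits". SAP 5.4 adds that if patients are randomised but not treated, "then they are by definition excluded from the efficacy and safety analyses as actual treatment is missing".

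**When the window opens.** SAP 7.2 says "Any adverse events occurring following start of treatment will be counted as treatment emergent". SAP 7 says "The start of treatment (Day 1) is defined as the date on which a patient receive the first study treatment", and its baseline definition identifies study drug administration as the "first full plasma exchange or sham treatment in the control group".

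**When the line goes in.** Protocol 5.1.3 allows peripheral or central access. If central, a double-lumen subclavian or jugular catheter must be in place before the first session. Protocol 6.2.1 adds: "It is advisable to place the catheter a few days before the first plasma exchange session". Protocol 5.2.2.5 lists what may be seen: "Pneumothorax, hemothorax, bleeding at the time of placement and thrombosis in the case of indwelling catheters" that stay in for long periods. In the control arm, Protocol 3.4 and Appendix 9 replace this with a non-invasive simulation.

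**The concern.** Placing a large central line is one of the most invasive steps in this trial, and whether it is real depends on the randomised arm. Patients are randomised at the end of screening (Protocol 3.5), and staff must know the allocation to choose between a real and a simulated line. An injury at placement is thus a consequence of allocation and not a screening event. If the safety definitions open only at the first exchange, such injuries fall before the window, and they can occur only in the active arms. Leaving them out can only flatter those arms. Safety of the procedure is a stated secondary objective (Protocol 2, SAP 2.2).

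**Working it through.** No figure in the plan bears on this, so there is none to reproduce. The check is to follow a placement complication through the SAP's rules.

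**Case A: active patient, placement complication, never exchanged.** SAP 5.3 requires at least one exchange, so the patient is outside the safety set. SAP 5.4 describes treatment as attending post-baseline visits, but that does not rescue the patient: 5.3 still asks for an exchange. A control who attends the same week 1 visit is in the set.

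**Case B: active patient, placement complication, exchanged on a later day.** The patient is in the safety set, and the event has onset before Day 1.

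- *Treatment-emergent status:* no, under SAP 7 and 7.2.
- *Primary safety criterion and per-exchange tables (SAP 7.2.1, 7.2.2):* these count exchanges with an event, using onset up to 72 hours after the end of an exchange and, in 7.2.2, the most recent exchange. No exchange precedes a placement event, so it has nothing to attach to. This includes the 7.2.2 split of full exchanges by central and peripheral access.
- *Tables of all AEs and all SAEs (SAP 7.2.2):* not expressly limited to treatment-emergent events, so the event may appear. The SAP does not say.

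**Case C: line placed on the day of the first exchange.** SAP 7.2.2 assumes that an event on the date of an exchange occurred during or after it, so the event would be linked to that exchange. The gap needs placement on an earlier date, which Protocol 6.2.1 advises.

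**Scale (illustration only).** Planned randomisation is 364 at 1:1:1:1, so active patients = 364 × 3/4 = 273. The central-access share and the placement-complication rate are not in the documents; both are assumed. Expected patients with a placement complication = 273 × share × rate, with the number of lines rounded to whole patients:

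| Central share (assumed) | Active patients with a line | 1% rate | 3% rate | 5% rate |
|---|---|---|---|---|
| 25% | 68 | 0.7 | 2.0 | 3.4 |
| 50% | 136 | 1.4 | 4.1 | 6.8 |
| 100% | 273 | 2.7 | 8.2 | 13.7 |

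The chance of at least one such patient is 1 − 0.99^68 = 0.495 at the low corner and above 0.99 at the high corner. These counts combine cases A and B; the documents do not allow them to be split.

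**The case against.** The best reply is that little is truly hidden, and much of it stands.

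- **A reader might infer that every placement complication vanishes from the AE tables.** The documents do not support that. SAP 7.2.2 lists tables of all AEs and all SAEs, plus listings of deaths, SAEs and discontinuations, and restricts none of them to treatment-emergent events. Loss from these tables is certain only for patients who are never exchanged.
- **A reader might infer that the events are not collected.** Protocol 9.1.1 has all AEs during the study entered in the CRF, 6.2.2 records events since the last visit before each exchange, the SAE form in Appendix 4 offers screening as a study period, and 9.2 promises that all AEs will be tabulated in the final report. The gap is in the analysis definitions. SAP 6.1 also tabulates why randomised patients were not treated, though as disposition and not as an adverse event.
- **A reader might apply a complication rate to all 273 active patients.** At 1–3% that gives about 3 to 8, but it assumes that every active patient has a central line. Peripheral access is allowed, so this holds only at 100% central use.
- **A reader might infer that catheter harm as a whole is missed.** Infection or thrombosis with onset after the first exchange is captured, and the protocol ties thrombosis to long-dwelling lines.
- **A reader might infer that sham patients can have no placement event.** Appendix 9 gives them the site's usual premedication, shaving, antiseptic and an adhesive patch. Only invasive injury is ruled out.

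None of this answers case A, or the primary safety criterion in case B.

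**Conclusion.** The concern holds as a gap in the definitions, limited to central-access patients whose line is placed before the day of the first exchange. Two consequences follow directly from the SAP's wording: an active patient harmed at placement and never exchanged is not in the safety set, and a placement event in a patient later exchanged is neither treatment-emergent nor countable in the primary safety criterion or the per-exchange tables. A third point is an ambiguity: whether pre-Day-1 events enter the tables of all AEs and SAEs.

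For invasive placement injury, the bias can run only in favour of the active arms. Its size is unknown. The range of about 0.7 to 13.7 patients rests on an assumed 25–100% central access and an assumed 1–5% complication rate, and the number never exchanged would be some part of that. The definitional finding does not depend on these figures. It should be corrected before the analysis, but it does not touch the efficacy conclusions.

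**What to change.** 1. **Safety set (SAP 5.3, 5.4).** In all arms, include randomised patients who have real or simulated catheter placement, or a first exchange or sham visit. A wider trigger, such as any study procedure, would also admit patients through the obligatory baseline lumbar puncture and blur the start. The separate SAP 5.3 rule for controls under protocol Version 1.0, who had no sham, can stay.
2. **Treatment-emergent window (SAP 7, 7.2).** For safety, start it at the earlier of real or simulated placement and the first exchange or sham visit. Day 1 for efficacy visit slotting need not change.
3. **Tables (SAP 7.2.2).** State that the AE and SAE tables include events from that point.
4. **One added table.** Show events between catheter placement and the first exchange by arm and access route. Moving the window is not enough, because a criterion counted per exchange cannot hold an event that precedes all exchanges.

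The cost is SAP wording, one re-derived flag and one extra table.
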